An adverse event (AE) is defined as the occurrence of an undesirable medical incident occurring in a clinical trial subject who has been administered drugs. It is not necessary for the treatment to have a causal relationship with the adverse event.

Therefore, an AE is any undesirable and unintended sign (e.g., abnormal laboratory test level findings), symptom, or chronic illness which correspond chronologically with the use of the corresponding pharmaceuticals regardless of whether it is determined to be related to the pharmaceuticals.

2. SAEs

All SAEs related to this treatment will be collected for this research protocol. An SAE is defined as a case in which the following undesirable medical incidents occur from an unspecified dose.

1. If death is caused.
2. If the situation is life threatening.

“Life threatening” will be used to describe instances in which the subject encountered the risk of death at the time of the incident. It will be used for cases which were more severe than had been anticipated and could have caused death.

3. If hospitalization or an extension to an existing hospitalization period is required.
4. If persistent or significant handicap/disability is caused.
5. If a congenital anomaly/birth defect is caused.
6. If it corresponds to a significant medical incident which satisfies the following:

Intervention may be necessary to prevent the above clauses 1 – 5.

Even though the corresponding event was not immediately life threatening, was non-fatal, or did not cause hospitalization, it could have put the research subject at risk.

The case described or an equivalent case is included in Takeda’s list of medically significant AEs.

3. Severity of AEs

The categories of intensity (severity) are as classified below:

Mild:	The case is temporary and the subject can easily endure it.
Moderate:	The case causes discomfort to the subject and causes a hindrance to daily life.
Severe:	The case causes a considerable hindrance to the subject’s daily life.

4. Collection and Reporting of Adverse Events of Special Interest

The trial investigator must report pancreatitis, hypersensitivity reactions including Stevens–Johnson Syndrome, hepatic effects, bladder cancer, and other related adverse events of special interest.

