
Bladder Cancer: Bladder Cancer is an adverse event of special interest of pioglitazone. The patient must quickly notify the investigator if macroscopic hematuria or other symptoms related to urination (dysuria or overactive bladder) occur while the corresponding drugs are being administered. If a bladder cancer diagnosis is confirmed, it must be reported to Takeda.

Bladder Cancer Withdrawal Criteria:
 
 - If there is a patient with a medical history of bladder cancer or unexplained hematuria, risk factors for bladder cancer (age, smoking history, exposure to some surgeries/chemotherapy (e.g., cyclophosphamide or radiation therapy of the pelvic region)) must be evaluated before the start of treatment. Whether or not macroscopic hematuria is present must be evaluated before treatment.

 - The patient must quickly notify the investigator if macroscopic hematuria or other symptoms related to urination (dysuria or overactive bladder) occur while the corresponding drugs are being administered. The administration of the corresponding drug must be suspended while additional examinations are done to make a diagnosis. - The investigator must fill out the sections related to AE/SAEs in the CRF. - If a definite diagnosis of bladder cancer is made, the administration of the corresponding drug must be permanently suspended.

- If the administration of the corresponding drug is suspended in the subject because of suspension criteria related to bladder cancer, it must be recorded as an AE along with the reason for the suspension.
- An early termination review must be conducted along with monitoring for subjects who were suspended.

5. Collection and Reporting of SAEs

In the event that an SAE occurs during the AE collection period after the consent form has been signed, it must be reported in accordance with the following procedures:

The trial investigator must immediately fill out and sign a Takeda SAE Report Form in English on the first day of the incident or within 1 business day of the date the investigator was notified of the incident. As much information as possible should be fully included on the form and the form must include a minimum of the following information:

A brief explanation of the case and the reason for categorizing the case as a serious event.
Subject identification number
Name of the trial investigator
Name of the trial drug
Evaluation of the causal relationship

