Subjects who sign the trial subject consent form and participate in the trial but do not finish will be eliminated. The elimination of a subject can be determined at any time during the trial. Withdrawal of consent by the subject will also be considered as an elimination and the reason for the withdrawal of consent must be clearly recorded. Furthermore, if an adverse event and/or a serious adverse event occurs during the trial, the corresponding subject will be immediately eliminated from the trial.

8) Safety Evaluation Criteria (Including Side Effects), Evaluation Methods, and Reporting Methods

Data Safety Monitoring Plan (DSMP)

According to existing research results, this trial is expected to be low risk because of the possibility and

severity of risk and discomfort which could occur in this in trial. The principal investigator is planned to continuously monitor for this risk and discomfort. Safety monitoring for this research will be conducted during every visit through an oral interview, a physical exam, laboratory tests, *et cetera*. If any of these results correspond to an SAE, it will be reported to the IRB.

- If there are any deviations from the protocol, the investigator will report major deviations to the IRB within 15 days of the point at which he or she becomes aware of the deviation and if there are minor deviations, the investigator will gather incidents of minor deviations and report them to the IRB at least once a year.
- Adverse events and all other information relating to safety will be reported in a safety information summary report. If there are incidents related to safety, a summary of the accumulated non-individual data should be compiled and reported at least once every 6 months in the form of a summary.

- Cases related to danger to the research subjects or other persons in which the case is judged to be an unexpected problem or in which it is life threatening should be reported to the IRB within 7 days and within 15 days for all other cases.
- The principal investigator or the subinvestigator will collect data and safety information, examine major efficacy evaluation endpoints, and conduct continuous monitoring every 6 months after the start of research.

9) Data Analysis and Statistical Analysis Methods

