- Descriptive statistics (mean and standard deviation) are used to describe continuous variables of baseline demographic and biochemical parameters, and counts with percentages are presented for categorical variables of baseline demographic and biochemical parameters.
- The efficacy and safety analyses were based on the full analysis set population consisting of all the patients who received the investigational drug at least once.
- The demographic characteristics of subjects were analyzed using ANOVA for the continuous variables and the chi-squared (χ^2) test for the categorical variables.
- Efficacy endpoints at week 12 and week 24 were analyzed using ANCOVA model with Bonferroni (baseline value as a covariate) for continuous variables and Pearson chi-square test adjusted by Bonferroni for categorical variables.
- Missing data, which is an unavoidable occurrence in prospective studies, will be substituted for using the last observation carried forward (LOCF) method.
- A p value <0.05 will be considered to indicate statistical significance and the SPSS (Statistical Package for Social Sciences) Version 25.0 will be used for statistical analysis

10. Measures for the Protection of Research Subject Safety

1) Fundamental Measures to Ensure Research Ethicality

The Declaration of Helsinki (Revised 2013) and the ICH-GCP will be followed.

IRB approval is scheduled to be received before the start of this research. At the start of research after IRB approval, the research objectives and process will be sufficiently explained to the research subjects. An examination consent form will be received from persons who understand these and voluntarily choose to participate.

Prior to the start of the trial, the trial investigator must acquire the written approval of the institutional review board of the relevant trial institutions and/or regulatory commissions regarding the conduct of the trial and must send a copy to Takeda ([contact]). If alteration of the trial is necessary, the investigator must acquire the written approval of the institutional review board of the relevant trial institutions and/or regulatory commissions regarding the conduct of the trial and must send a copy to Takeda ([contact]).

As the research relates to human subjects, the investigators must register this trial at clinicaltrials.gov and any other relevant institutions if necessary.

2) Research Subject Consent Process

<Research Subject Consent Process>

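### Sections 9.1 and 9.7 remove a subject for any adverse event, however mild or unrelated; this ends scheduled HbA1c and safety visits and sits badly with the suspend-and-investigate handling in section 9.6

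*Protocol*

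**What the plan says.** The rule appears in identical words in section 9.1 (Specific Research Methodology) and section 9.7 (Suspension and Elimination Criteria): "if an adverse event and/or a serious adverse event occurs during the trial, the corresponding subject will be immediately eliminated from the trial". It names adverse events and serious adverse events separately, so it cannot be read as covering serious events only.

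Section 9.6 sets how wide the term is. Under Definition, an adverse event needs no causal link to treatment, may be an abnormal laboratory value, and counts "regardless of whether it is determined to be related to the pharmaceuticals". Under Severity, the lowest grade is described as "The case is temporary and the subject can easily endure it".

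The same section handles particular events in steps:

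- **Bladder symptoms** (Bladder Cancer Withdrawal Criteria): "The administration of the corresponding drug must be suspended while additional examinations are done to make a diagnosis". Then: "If a definite diagnosis of bladder cancer is made, the administration of the corresponding drug must be permanently suspended". A suspension on these grounds is recorded as an adverse event, and "An early termination review must be conducted along with monitoring for subjects who were suspended".
- **Hepatic findings** (Precautions for Alogliptin, item 3): drug is suspended and the cause is looked for. Restart is barred where no other explanation is found.

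Section 9.9 bases efficacy and safety on a full analysis set "consisting of all the patients who received the investigational drug at least once", with missing data "substituted for using the last observation carried forward (LOCF) method". After baseline, HbA1c is measured only at Weeks 12 and 24.

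**The concern.** A mild, unrelated complaint in Week 2 meets the protocol's definition of an adverse event and so ends participation. No text keeps an eliminated subject in the Week 12 or Week 24 assessments. The values are never collected, and no later analysis plan can recover them.

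Three things are at stake.

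- **Scheduled data.** HbA1c, laboratory and adverse event assessments at the planned visits stop after the first event. Follow-up of serious events, follow-up of precaution-listed symptoms, bladder monitoring and the 30-day call continue. The loss is therefore clearest for non-serious events.
- **Conduct.** An investigator with an abnormal liver test is told in one place to suspend, investigate and possibly restart, and in another to remove the subject at once. The nine listed institutions may settle this differently.
- **Comparability.** The trigger comes after randomisation in an open-label trial and may differ by arm. Section 6.1 reports more hypoglycemia with a sulfonylurea than with a DPP-4 inhibitor, and section 9.6 names sulfonylureas as a known cause. If early exits count as zero change, more exits on glimepiride would make it look less effective without any true difference.

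**Working it through.** **Step 1: the texts side by side.**

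| Situation | Section 9.6 | Sections 9.1 and 9.7 |
|---|---|---|
| Mild or unrelated event, abnormal laboratory value | Is an adverse event; record and grade | Eliminate at once |
| Abnormal liver tests | Suspend, investigate; restart barred if no other cause is found | Eliminate at once |
| Hematuria or urinary symptoms | Suspend for work-up; permanent stop on definite diagnosis; termination review and monitoring | Eliminate at once |

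The hepatic row is the clear clash: a conditional bar on restart makes sense only if some subjects may restart. The bladder row is weaker. A suspension that becomes permanent only on diagnosis suggests that it may be temporary, but the text never says that drug resumes, and it asks for an early termination review.

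**Step 2: the plan's sample size (section 8.3).** Inputs: alpha 0.05/3 two-sided, power 0.90, SD 1.037 in both arms, mean changes -0.96 (alogliptin) and -1.71 (combination).

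n = 2 × 1.037² × (2.394 + 1.282)² / 0.75² = 51.65, or 52 per arm against the stated 53. This reproduces. The target of 66 implies an allowance of 1 − 53/66 = 19.7%.

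**Step 3: illustrative power.** All exit rates q are assumed. The calculation uses 66 per arm and a noncentral t on the unadjusted change, which approximates the planned ANCOVA.

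- *Zero change:* exit before Week 12 with baseline carried forward. The change is 0 with probability q, so the mean is (1−q)μ and the variance is (1−q)·1.037² + q(1−q)μ².
- *Half late:* half of exits come after Week 12 and carry the full effect, so q is replaced by q/2.
- *Left out:* n = 66(1−q).

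| q in both arms | Difference, zero change | Power, zero change | Power, half late | Power, left out |
|---|---|---|---|---|
| 10% | 0.675 | 0.884 | 0.925 | 0.933 |
| 20% | 0.600 | 0.776 | 0.884 | 0.898 |
| 30% | 0.525 | 0.648 | 0.834 | 0.848 |

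Worked case, q = 20%, zero change: difference 0.75 × 0.8 = 0.600; SDs 1.004 and 1.152; SE = √((1.004² + 1.152²)/66) = 0.188; noncentrality 3.19; power 0.776.

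Part due to this rule: with 5% early exit from other causes, adding 5, 10 or 15 points moves power from 0.925 to 0.884, 0.834 or 0.776 (zero change), or from 0.946 to 0.933, 0.917 or 0.898 (left out).

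**Step 4: illustrative false-positive rate.** There is no true difference and exit is unequal; the nominal rate is 0.0167. The protocol gives no glimepiride mean, so two values are used: -0.96, borrowed from alogliptin, and -0.50, an assumption.

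| Exits | Mean change | 10% vs 20% | 10% vs 30% |
|---|---|---|---|
| All before Week 12, zero change | -0.96 | 0.033 | 0.097 |
| All before Week 12, zero change | -0.50 | 0.021 | 0.038 |
| Half late | -0.96 | 0.021 | 0.033 |
| Left out, exit unrelated to HbA1c (simulated) | -0.96 | 0.0167 | 0.0169 |

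For the first row, the spurious differences are 0.96 × (0.20 − 0.10) = 0.096 and 0.96 × (0.30 − 0.10) = 0.192, with SEs of 0.177 and 0.174.

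**The case against.** The strongest reply is that nobody intends the literal rule. The protocol schedules adverse event recording at every visit and grades events from mild upwards, which would be odd if the first event ended participation. Section 9.7 also says elimination can be decided at any time, which is the language of judgement. Wording slips nearby (a two-armed trial with three arms, a 2 mg alogliptin dose) make a missing qualifier plausible. That may well be so, but it is inference. The sentence stands unqualified in two sections, and sites follow the text.

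Three stronger readings are tempting, and the documents do not support them.

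- *A flat contradiction with the bladder criteria.* Those criteria govern drug, sit under a withdrawal heading, never mention resuming, and require a termination review. Suspending drug and leaving the trial can both be carried out. The hepatic text carries the conflict better.
- *Data are discarded.* Section 9.9 keeps every dosed patient and fills gaps by LOCF. What stops is collection after the event. The word for elimination could be read as exclusion from analysis, but the protocol does not say so.
- *The trial is underpowered or biased by a known amount.* No event rate is given. The cited hypoglycemia comparison concerns glipizide and sitagliptin, while glimepiride is capped at 2 mg here. If such subjects are left out, 20% exit leaves power at 0.90, as planned. Power loss from early exit under LOCF is not specific to this rule, which only adds avoidable exits.

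The point that off-drug Week 24 values may drift towards no change also stands: keeping visits would not remove every effect of unequal stopping.

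**Conclusion.** The point holds and should be fixed. That the rule is unlimited, and that it conflicts with the hepatic handling, follows from the text and needs no assumption. The looser tension with the bladder handling is real but partly relieved by the termination review. The loss of scheduled HbA1c and safety assessments follows if the rule is applied as written.

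The size is not established. With baseline carried forward and all exits before Week 12, the false-positive rate is about 0.02 to 0.03 for 10% versus 20% exit and about 0.04 to 0.10 for 10% versus 30%, over mean changes of -0.50 to -0.96. Later exits lower these figures. Leaving such subjects out returns the rate to nominal if exit is unrelated to HbA1c. The protocol does not say whether baseline may be carried forward. The figures show what the rule could do, and should not be read as a forecast for this trial.

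**What to change.** In both sections, replace the sentence with:

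> Study drug is suspended or stopped for adverse events that under section 9.6, or in the investigator's judgement, make continued drug unsafe; other events are recorded and treatment continues. Stopping drug for an adverse event does not by itself end participation: consenting subjects keep the scheduled Week 12 and Week 24 HbA1c and safety assessments and the 30-day call, and are analysed in their assigned arm. Drug-free time after such a stop does not count toward the 80% compliance rule, and such a stop is not a failure to finish.

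The last sentence is needed because stopping drug could otherwise remove the subject through the compliance or non-completion rules. The Week 12 HbA1c rule and LOCF stay as they are; the change works by supplying measured values, so that fewer need filling in.

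Cost: an amendment of a few sentences, IRB approval at the nine listed institutions, and possibly a revised consent form, which section 10.2 also puts before the IRB. No visits are added. Some Week 24 values will be taken off drug or on alternative treatment, so the comparison reflects assignment more than drug taken throughout. Subjects who stop for an adverse event will be treated differently from other poor compliers.

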 $\sigma_1 = 1.037, \sigma_2 = 1.037$
 $\mu_1 = -0.96, \mu_2 = -1.71$

According to the above formula, the number of sample collections was calculated for treatment groups of 53 subjects each. However, in consideration of the dropout rate, there is a target of 66 subjects for each treatment group. The dropout rate was estimated on the basis of the dropout rates of existing prospective studies.

4) Research Subject Recruitment Plans

For the recruitment of research subjects for this research, patients who are characteristic of the selection criteria and are currently receiving the outpatient treatment of the principal investigator and the joint investigators who are in accordance with the selection criteria will be recruited. The principal investigator and joint investigators of this research will not exclude any patient who could participate in this research on the basis of ethnicity or socioeconomic status.

9. Research Method

1) Specific Research Methodology

[figure not shown]
- ① The research subjects selected for this trial will patients among those who have given their approval to participate in the trial and who are first starting their treatment or who intend to alter their medication because treatment with the existing drugs has failed who satisfy the criteria.
 - ② Patients with a '7.5% ≤ HbA1c ≤ 10%' in the HbA1c test will be chosen.
 - ③ Patients who are intending to change drugs due to the failure of an existing drug treatment must have the use of 1,000 mg or the maximum tolerance dose (MTD) of metformin recorded in his or her medical records.
 - ④ The investigators must confirm the patient's intention to participate in the trial and, starting at the point of the routine laboratory test results, must provide a sufficient explanation of this research to the patients who satisfy the criteria and then must acquire a research subject consent form from these patients. The consent forms must include the trial objectives, the benefits for participants, the risk factors, a confidentiality agreement, the right to withdraw consent, and contact information. The patients must sign the consent forms.
- The change in the level of HbAc1 will be compared among the 3 treatment groups – the glimepiride monotherapy treatment group, the alogliptin monotherapy treatment group, and the alogliptin - pioglitazone combination therapy treatment group – until the 24th week after the Baseline is taken.
 - MAGE will be checked to investigate changes in blood glucose.

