 - Glimepiride's nonproprietary name is glimepiride; this drug is a snowman shaped tablet. Starting with a 1 mg dosage once a day before the first meal, the investigators will decide to increase the dosage to a maximum of 2 mg in the Week 4.
 - Dosage adjustment will be conducted for participants proven to have persistent hyperglycemia (in the opinion of the investigator).

[figure not shown]
	Week 4	Week 12
--	---------------	----------------

Alogliptin 25mg	Dosage adjustment is not allowed	Dosage adjustment is not allowed
Glimepiride	1mg → 2mg	Dosage adjustment is not allowed
Alogliptin 25mg +Pioglitazone 15mg	Dosage adjustment is not allowed	Dosage adjustment is not allowed

- Alogliptin’s nonproprietary name is alogliptin benzoate and is an oval-shaped yellow tablet. A 25 mg dose of this medication is administered once a day and is taken with food or on an empty stomach.
 - The pioglitazone used by the alogliptin - pioglitazone combination therapy treatment group is pioglitazone hydrochloride and is a grey circular tablet. A 15 mg dose of this medication is administered once a day and is taken with food or on an empty stomach.
 - The subjects will test the HbA1c level in Week 12 and Week 24 and will check CGMS at the Baseline and in Week 24.
 - General characteristics (bodyweight and BMI), vital signs, and laboratory tests will be conducted in Week 4, Week 12, and Week 24.
 - MAGE will be measured using CGMS (continuous glucose monitoring system) for 3 days (72 hours). Education regarding eating, CGMS usage, notices, and correction will be given.
 - A follow-up safety survey will be conducted 30 days after the last visit.
 - Subjects will be enrolled in the trial for 6 months and following this a follow-up survey will be conducted.
 - Approximately 12 months will be required for the total trial period based on the last patient (6 months) to have their Baseline enrollment conducted.
 - Patients will be asked to come to the clinical research institution after Week 4, Week 12, and Week 24 (for Week 12 and Week 24, a period of ±7 days is permitted) after the Baseline (or the first) visit. In addition, patients will be requested to take a call 30 days after their last visit for the safety follow-up survey.
 - Subjects with a drug compliance of less than 80% will be eliminated.
 - Subjects with an HbA1c level of more than 9.0% in Week 12 will be eliminated.

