information to determine the cause, there are post market reports of fatal and non-fatal hepatic failure in patients who took NESINA [reference Adverse Drug Events (6.2)]. In a randomized, controlled trial, an increase in the of the serum alanine aminotransferase (ALT) of 3 times the upper limit of normal (ULN) was observed in 1.3% of patients receiving alogliptin treatment and 1.5% of the patients in all control drug treatment groups. Type 2 diabetes patients can suffer from fatty liver disease, which can cause abnormal findings in hepatic function tests. These patients can also have other forms of liver disease and most of these cases of liver disease can be cured or managed. Therefore, it is recommended that the results of the hepatic function test be collected and that the patient be evaluated before starting

NESINA treatment. In patients with abnormal hepatic function test findings, extreme care must be taken when starting NESINA treatment. A hepatic function test should be run promptly if there is a patient with symptoms which could indicate liver damage (including fatigue, loss of appetite, abdominal discomfort, dark urine, or jaundice). In this clinical context, if it is confirmed that the patient has a clinically significant increase in the levels of hepatic enzyme or that the hepatic function tests continue to show abnormal findings or have worsened, NESINA treatment must be suspended and an investigation into the possible causes must be conducted. If there are no other explanations for the abnormal hepatic liver function test findings, the patient may not restart treatment with NESINA.

4) Use of Medication Known to Cause Hypoglycemia: Insulin and insulin secretagogues (e.g., sulfonylureas) are known to cause hypoglycemia. Therefore, a smaller dose of insulin or insulin secretagogues must be used to reduce the risk of hypoglycemia when these drugs are taken in combination with NESINA.

5) Macrovascular Outcomes: There are no clinical trials which show conclusive evidence of how to reduce macrovascular risks when NESINA or other diabetes treatments are administered.

- Precautions for Pioglitazone

Actos must be used with caution in the following patients:

- 1) Combination therapy with other oral hypoglycemic agents
- 2) Premenopausal women
- 3) Edema

7) Suspension • Elimination Criteria

Subjects with a drug compliance of less than 80% will be eliminated.

Subjects with an HbA1c level of more than 9.0% in Week 12 will be eliminated.

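### On this visit schedule, LOCF scores patients lost before Week 12 as zero HbA1c change, which mainly shrinks the Week-24 difference the trial is sized on

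*Protocol*

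**What the plan says.** Section 9, item 9 (Data Analysis and Statistical Analysis Methods), and the matching entry in the Research Outline give one rule for missing data: "Missing data, which is an unavoidable occurrence in prospective studies, will be substituted for using the last observation carried forward (LOCF) method". Efficacy is analysed in the "full analysis set population consisting of all the patients who received the investigational drug at least once", with no requirement for a post-baseline value. The Week-12 and Week-24 endpoints go into an ANCOVA with baseline as covariate and a Bonferroni correction.

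Section 9, item 1, sets the measurements: "The subjects will test the HbA1c level in Week 12 and Week 24 and will check CGMS at the Baseline and in Week 24". Table 1 in Section 9, item 4, agrees and shows no HbA1c at Week 4.

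Section 9, items 1 and 7, list reasons for removal that can act before Week 12. One is low compliance: "Subjects with a drug compliance of less than 80% will be eliminated". Another is any adverse event: "if an adverse event and/or a serious adverse event occurs during the trial, the corresponding subject will be immediately eliminated from the trial".

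Section 8, item 3, calculates 53 patients per arm and then states that "in consideration of the dropout rate, there is a target of 66 subjects for each treatment group". It gives neither the dropout rate nor its timing or split by arm.

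**The concern.** LOCF needs an earlier post-baseline value to carry, and this schedule has only one HbA1c measurement between baseline and the endpoint. A dosed patient who leaves before Week 12 has nothing after baseline. The protocol does not say outright that baseline is then carried, but no other reading keeps the patient in the stated analysis set. The change from baseline is therefore exactly zero. The same happens to every missing Week-12 HbA1c, which is a secondary endpoint, and to every missing Week-24 CGM value. If only post-baseline values may be carried, these patients drop out of a set defined by one dose, and the text contradicts itself.

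The arm with the larger true fall loses more from each zero. The planned difference therefore shrinks even when loss is equal, and shrinks further if the combination arm loses more patients early. The trial is open label, so loss may well differ by arm. With no true difference, unequal early loss can also create one.

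Patients removed because Week-12 HbA1c exceeds 9.0% are a separate matter. They have a Week-12 value, and LOCF carries that poor value to Week 24.

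**Working it through.** **Inputs from Section 8, item 3:** SD of change 1.037 in both arms; mean changes -0.96 (alogliptin) and -1.71 (combination), difference 0.75; alpha 0.05/3 two-sided (z = 2.394); power 90%; 53 per arm, raised to 66.

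**Assumptions:** dropout split and timing; a Week-12 effect that is a fraction f = 0.8-1.0 of the Week-24 effect; baseline-change correlation from 0 to -0.5; loss unrelated to outcome.

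**The plan's own figure.** n = 2 × 1.037² × (2.394 + 1.282)² / 0.75² = 51.65, so 52 per arm. This is close enough to the stated 53. The implied dropout is (66 - 53)/66 = 13/66 = 19.7%.

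**Expected difference under LOCF.** With dropout d and early share e, an arm's mean change is (1 - d)μ + d(1 - e)fμ, since early losses contribute 0.

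- Equal 19.7%, all early: 0.75 × (1 - 0.197) = 0.602.
- Equal 19.7%, half early: 0.75 × (0.803 + 0.0985f) = 0.661-0.676.
- 15% alogliptin v 25% combination, all early: 0.75 × 1.71 - 0.85 × 0.96 = 1.2825 - 0.816 = 0.467.
- 15% alogliptin v 5% combination, all early: 0.95 × 1.71 - 0.85 × 0.96 = 1.6245 - 0.816 = 0.809.

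When all loss is early, the difference grows only if loss on alogliptin exceeds 1.71/0.96 = 1.78 times that on the combination.

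**Power.** When all loss is early, an arm's variance is (1 - d) × 1.037² + d(1 - d)μ². With equal 19.7% loss this is 1.009 and 1.326. The standard error is √((1.009 + 1.326)/66) = 0.188, and unadjusted power is Φ(0.602/0.188 - 2.394) = 79%.

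Baseline-adjusted power comes from a two-arm ANCOVA simulation (40,000 replicates per cell, 66 per arm). Ranges cover the assumed f and correlations.

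| Loss, alogliptin / combination | Timing | Difference | ANCOVA power |
|---|---|---|---|
| 19.7% / 19.7% | all before Week 12 | 0.60 | 78-85% |
| 19.7% / 19.7% | half before Week 12 | 0.66-0.68 | 87-94% |
| 19.7% / 19.7% | none before Week 12 | 0.72-0.75 | 94-99% |
| 15% / 25% | all before Week 12 | 0.47 | 50-58% |
| 15% / 25% | half before Week 12 | 0.58-0.61 | 75-88% |
| 15% / 5% | all before Week 12 | 0.81 | not computed |
| 15% / 5% | half before Week 12 | 0.78-0.79 | not computed |

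**Same losses without LOCF.** All loss is early and missing at random. ANCOVA on the observed patients, to which the proposed methods approximately reduce here, was run with 8,000 replicates. The difference is 0.74-0.75. Power is 89-97% with equal 19.7% loss and 89-96% with 15% v 25%.

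**No true difference, 10-point gap in loss.** When both arms share mean μ and all loss is early, LOCF creates a difference of 0.10 × |μ|, that is 0.096 or 0.171. Pairwise false positives, against 1.67% nominal, are:

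- all early: 3.4-6.7% unadjusted, 3.4-7.7% with ANCOVA;
- half early: 2.1-3.4% unadjusted, 2.0-3.9% with ANCOVA;
- equal 20% loss: 1.6-1.7% with ANCOVA, so no inflation;
- without LOCF, 15% v 25% all early: 1.6-1.8%.

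**Post-baseline-only reading.** The arm mean becomes ((1 - d)μ + d(1 - e)fμ)/(1 - de). The difference is 0.72-0.75 with equal 19.7% loss and 0.69-0.75 with 15% v 25%.

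**The case against.** - **Baseline carry-forward is a reading.** A SAP, which is not at hand, might specify it, and if only post-baseline values are carried the shrinkage nearly disappears. This is fair, but that reading removes dosed patients from a set the protocol defines by one dose, so the text needs repair either way.
- **The large losses of power are corner cases.** LOCF keeps 66 per arm where about 53 are needed, so with equal loss, half of it early, power stays near plan. The 50-58% figure needs both an unequal split and all loss before Week 12. This stands and limits the size of the finding.
- **The Week-12 HbA1c above 9.0% rule is left out of the main figures.** Those losses are never early, and they may take up part of the 19.7% allowance. Under assumed baseline values, adding the rule with 5-10% early loss in both arms gives 0.69-0.74 and 88-96% power. With 19.7% early loss it still gives 0.63 and 79-83%; with 10% v 20% early loss, 0.52-0.53 and 61-65%. The rule softens the effect without removing it.
- **The benchmark is uncertain.** The planned means carry no stated missing-data method. If they came from an analysis with carried values, some shrinkage is already built in. The protocol cannot settle this.
- **Zero change can be a deliberate conservative score** after stopping for an adverse event. That is a legitimate target, but the protocol does not state it. Here the zero follows from the visit schedule and applies to early losses for any reason.

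**Conclusion.** The concern holds and should be fixed. The stated rule, set and schedule together score early losses as zero change, and this mainly pulls the sized difference toward zero. With equal loss at the implied 19.7%, 0.75 falls to between 0.60 (all early) and 0.72-0.75 (none early). Planned power is missed mainly when most loss is early, and more seriously when the combination arm loses more. Exaggeration is possible but small: at most 0.81 among the 10-point gaps tried. False positives rise modestly, and only when loss is unequal.

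Confidence in the size is medium. Timing and split of dropout, the Week-12 effect and the baseline correlation are all assumed, and 0.75 is taken as the effect without carried values because the protocol does not say which effect it targets. Comparisons with glimepiride cannot be computed, since no mean change is given for that arm.

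**What to change.** Replace LOCF as the primary method in Section 9, item 9, and in the Research Outline. Either of these would serve:

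- ANCOVA after multiple imputation that includes every dosed patient and uses baseline and Week-12 HbA1c; or
- a longitudinal model with baseline, Week-12 and Week-24 HbA1c all as outcomes.

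Both keep patients with no post-baseline value in the stated population. A model for post-baseline change alone would omit them. Use multiple imputation for Week-24 CGM too, although with no intermediate CGM value it will add little to a completers' analysis.

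Keep two sensitivity analyses: LOCF, stating that baseline is carried when nothing later exists, and return-to-baseline imputation.

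The cost is wording only, with no new visits or data. The primary result would then assume missing at random and describe the effect had patients stayed on treatment. That may not hold for patients removed for adverse events, and the return-to-baseline analysis is there to test it.
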